This is a randomized controlled trial assessing the success of external cephalic version (ECV). When patients are noted to be in breech presentation (bottom of baby facing down) at 37 weeks gestation they are encouraged to undergo an ECV procedure (an external rotation done by the obstetrician) which rotates the baby to a cephalic presentation (head facing down) in order to allow for vaginal delivery. Patients who fail this procedure undergo a cesarean section if the baby has still not rotated by the time of delivery. At our institution, this is usually done by giving a tocolytic (relaxant to the uterus) and performing the procedure. In rare cases the patient may be offered spinal anesthesia, particularly when the attempt was unsuccessful without anesthesia and the provider believes that anesthesia will facilitate success or if the patient is not tolerating the procedure due to pain. Randomized control studies and a recent meta-analysis have suggested that spinal anesthesia increases the success rate of ECV significantly and decreases the number of cesarean sections. However, there have been limited studies on using spinal anesthesia only if the procedure fails without it. Our study aims to randomize patients who present for ECV into two groups. Group 1: patients who receive spinal anesthesia immediately and Group 2: patients who receive spinal anesthesia only if the procedure first fails without it. Comparing these two groups is essential in order to optimize ECV procedure protocols with the highest success and least invasive approach.

IF Number

IF1989320

2. Summary - Setup

Funding Has Been Requested / Obtained	No
Application Type	Request to Rely on Mount Sinai IRB
Research Involves	Prospective Study ONLY
Consenting Participants	Yes
Requesting Waiver or Alteration of Informed Consent for Any Procedures	No
Humanitarian Use Device (HUD) Used Exclusively in the Course of Medical Practice	No
Use of an Investigational Device to Evaluate Its Safety or Effectiveness	No
Banking Specimens for Future Research	No
Cancer Research that Requires Approval from the Protocol Review and Monitoring Committee (PRMC)	No
Clinical Trial	Yes

**** A prospective biomedical or behavioral research study of human subjects that is designed to answer specific questions about biomedical or behavioral interventions (drugs, treatments, devices, or new ways of using known drugs, treatments, or devices).***

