There is no anticipated research related harm for study subjects. There is a very small risk of adverse outcomes inherent in the procedures themselves, but this is not due to participating in research. Medical personal will be readily available for any adverse outcome as is standard for all pregnant patients in such events.

Expected Direct Benefit to Subjects

Each subject may be expected to directly benefit from participation in this study. For those that are in the immediate spinal group, these patients may benefit from less discomfort (as is noted in prior studies) and an increased external cephalic version success rate (compared to controls). Those who are in the spinal anesthesia only if ECV fails without it, may benefit from not having to undergo an additional procedure (neuraxial anesthesia) when attempt leads to cephalic presentation with ease. It is unclear if these patients will have the same ECV success rate, but prior non-randomized trials do suggest this finding.

Benefit to Society

The results of this study may benefit society in that a better protocol may be in place for ECV attempts that increases the rates of success without increasing the rate of risk or cost.

Provisions to Protect the Privacy Interests of Subjects

The patients will be approached by the a member of the study team on the labor floor to determine if they are willing to be included in the study. Their participation will not require any additional examinations. They will only be approached once by the study team on the labor floor to determine if they are willing to participate. All research-related discussions will be held in the patient's private room. Any questions will be answered and fully discussed to maximize patient comfort. Patients will be allowed time to consider participation and we will explain to patients that we will follow up their delivery information, but will not contact them directly. We will also assure the patient all the steps that will be taken to protect their privacy.

Economic Impact on Subjects

We do not see any foreseeable additional costs to subjects for participating in this research study. The patient is already in the hospital to undergo a version and anesthesia may or may not be used for this procedure even when not participating in the study.

11. Subjects - Pregnant Women

**Preclinical Studies Including Those No
on Pregnant Animals and Clinical
Studies Including Those on Non-
Pregnant Women Have Been
Conducted**

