There are two procedures possibly being performed. In terms of the ECV, all patients will undergo an ultrasound examination as is necessary to confirm the malpresentation of the fetus and rule out any anomalies that would complicate a vaginal delivery. If found to have malpresentation patients will be placed on a fetal monitor and isotonic solution will be administered via IV. A CBC and type and screen will be drawn and sent. The patient will then be consented for the external cephalic version, as this is the procedure that the patient has come to the hospital for, and will be performed regardless if they participate in the study. After this, they will be asked if they would like to participate in a study. If so, a member of the research team will approach the patient and consent the patient for the study. If the patient consents and is randomized to Group 1, the patient will have a spinal administered by the on call anesthesiologist using standard protocol (intrathecal bupivacaine 7.5 mg). The patient will then be administered 0.25 mg Terbutaline subcutaneously and the ECV will be attempted. Under ultrasound guidance the provider will attempt to lift the breech upward from the pelvis with one hand and guide the head with the other hand to produce a forward roll. If forward roll fails, a backward roll somersault may be attempted. ECV attempt will be abandoned if there is significant fetal bradycardia, discomfort to the patient, or if the procedure cannot be completed easily with these maneuvers. Once attempt is complete, whether successful or not, the patient will be monitored for a minimum of 30 minutes, and will be discharged once they are able to walk, void, and tolerate PO intake, only if fetal and maternal status is reassuring. If the patient is randomized to Group 2, the patient will be administered terbutaline 0.25 mg subcutaneously and the version will be attempted using the same procedure as above. If successful, the patient will be monitored for 30 minutes and discharged if fetal and maternal status is reassuring. If the attempt fails, the patient will be administered spinal anesthesia as above and the same maneuvers will be attempted. Once attempt is complete, whether successful or not, the patient will be monitored for a minimum of 30 minutes, and will be discharged once they are able to walk, void, and tolerate PO intake, only if fetal and maternal status is reassuring.

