Description of the Source Records that Will Be Used to Collect Data About Subjects

In order to collect data about the procedure, a member of the research team will fill out a questionnaire at the time of procedure and all questionnaires will be placed in a locked cabinet in the PI's office in Mount Sinai West- Suite-10C. All other data about delivery and demographics will be collected after the procedure using labor and deliveries' electronic medical record system (Peribirth).

Description of Data that Will Be Collected Including Long-Term Follow-Up

Protected Health Information (PHI) will be collected and used in the study. No PHI will be disclosed. Only study personnel will have access to subject information. The study investigators will collect medical information about the subject over the course of the study. Study data will be entered into a de-identified research secure password-protected database, using a unique code numbering system. A code number linked to subject identity will be used instead of names. The code number will not be derived from any patient identifiers, such as patient name or medical record number. The record linking the subjects' name with their assigned codes will be kept on a password protected file on a secure departmental drive. Only the PI will have access to this file. All study forms will be kept private and stored in a locked file cabinet in a secure location in the office of the PI. The secure computerized research database will be on a password-protected file within the OB/GYN department at Mount Sinai West. The linked code and dates of service are the only patient identifiers to be collected onto the computerized database spreadsheet along with the subject's medical information needed for the purposes of the study. Once data collection and analysis is completed, the linked code and data will be deleted.

Research Requires HIV Testing

13. Procedures - Genetic Testing

Genetic Testing Will Be Performed No

14. Procedures - Details**Surveys or Interviews** Yes**Type of Instruments Being Used** Created By Research Team**Description of Instruments Created By Research Team**

The research team has created a questionnaire that will be filled out by the person performing the procedure once the procedure is completed. This questionnaire will then be collected by the PI and stored in a locked cabinet in the PI's office.

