Audio / Photo / Video Recording No**Deception** No**Results of the Study Will Be Shared with Subjects or Others** No

15. Procedures - Instruments**Instruments Created By Research Team**

Type	Questionnaire
Name	Questionnaire
Upload	Study form.docx

16. Procedures - Compensation

Compensation for Participation No

17. Consent - Obtaining Consent

Consent Process Adult Consent

Where and When Consent Will Be Obtained

External cephalic versions are scheduled each day by the patients' primary obstetrician. If a patient is found to be eligible for the study, an investigator will approach the patient once they are admitted for their external cephalic version on labor and delivery. A member of the research team will then review the consent with them. The investigator will give the potential subject the opportunity to ask any questions and have them answered. They will be given the opportunity to think about the study. (Only those investigators listed as study personnel and authorized to obtain consent, will obtain informed consent). Once a patient wishes to join the study and informed consent is obtained, the subject can participate. Each subject will receive a signed copy of the consent form. The subject can withdraw from the study at any time without any retribution.

Waiting Period for Obtaining Consent

The patient will be given as much time as they need to consider consenting for the study. Each patient that is admitted for an external cephalic version is placed on the fetal monitor and given 1-2 liters of isotonic solution prior to the procedure (this is routine at our institution). They will be given that amount of time (usually 30 minutes-1 hour) to decide if they would like to take part in the study. If they need more time, then we will wait until the patient has felt that they have had adequate time to decide if they would like to participate.

SOP HRP-090 Informed Consent Process for Research Is Being Used Yes

Process to Document Consent in Writing Will Use Standard Template

Non-English Speaking Participants Will Be Enrolled Yes

What Languages Other Than English Will Be Used

Any language can be used as long as an approved interpreter is available for that language at the time of consent. We will follow the Short Form Policy regarding proper consent and interpreters.

What Process Will Be Used Short Form

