Attest that you will follow the Short Form Policy ([insert link]), including the Hospital policy (A3-105 at ISMH and HHC Administrative Policy ADM 30 at Elmhurst/Queens) regarding approved interpreters.

18. Consent - Documents**Consent Documents**

Type	Consent
Name	Consent
Upload	Consent2(unmarked).doc

19. Data - Collection

Health Related Information Will Be Viewed, Recorded, or Generated Yes

Description of Health Information That Will Be Viewed, Recorded, or Generated

Primary outcome data to be collected includes: successful external cephalic version. Other information that will be recorded includes: name, MR #, ultrasound findings, patient pain score (1-10) from procedure, score for ease of performing the procedure, complications from procedure, delivery mode, 5 minute, Apgar score <7, arterial cord pH <7.2, NICU admission. Demographic data will also be collected such as age, race, BMI, parity, and medical disease.

Non-Health Related Information Will Be Viewed or Recorded No

HIV / AIDS Related Information Will Be Viewed or Recorded No

Data That Will Be Viewed, Recorded, or Generated Contains ANY of the Following Directly Identifiable Information Yes

Will Be Viewed Name, Medical Record Number

Will Be Recorded Name, Medical Record Number

Data Collection Sheet

A Data Collection Sheet is required if you are either performing a retrospective review, or your study meets the category of exempt 4 research, or your study meets the category of expedited 5 research. Please upload it here.

Data Collection Source(s) Participant, Medical Chart (Paper or Electronic)

20. Data - HIPAA

Obtaining HIPAA Authorization Yes

How PHI Will Be Protected from Improper Use or Disclosure

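### Does the 1-10 pain score need a stated attempt or time point for Group 2 patients who have a second attempt under spinal?

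*Combined protocol and SAP*

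**What the plan says.** Section 3 (Primary and Secondary Study Endpoints) names patient discomfort among the secondary outcomes, with no instrument or timing. Section 19 gives the only measure: "patient pain score (1-10) from procedure, score for ease of performing the procedure, complications from procedure". The same section gives "Data Collection Source(s) Participant, Medical Chart (Paper or Electronic") as the data sources. The pain score is also listed apart from the operator's ease score, so it is most naturally the patient's own rating.

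Section 12 (Description of Procedures Being Performed) gives Group 2 a first attempt without spinal and continues: "If the attempt fails, the patient will be administered spinal anesthesia as above and the same maneuvers will be attempted". Group 1 has its spinal before any attempt. The same section lists patient discomfort among the reasons to abandon an attempt.

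Two places describe the questionnaire. Section 12 (Description of the Source Records) says "a member of the research team will fill out a questionnaire at the time of procedure". Section 14 says "The research team has created a questionnaire that will be filled out by the person performing the procedure once the procedure is completed". Section 15 and the attachment list in section 24 name the form, "Study form.docx", but its content is not in the available text.

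Section 21 (Data Analysis Plan) assigns continuous variables to a two-tailed t-test and categorical variables to a chi-square test, at 0.05. It has no rule for a patient with two attempts.

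**The concern.** Pain is expected to differ between an attempt with spinal and one without. Section 10 names lower discomfort as a benefit of immediate spinal: "these patients may benefit from less discomfort (as is noted in prior studies)". If a rescued patient's score can refer to the first attempt, the last attempt or the whole stay, the arm comparison depends on which was recorded. The ambiguity falls on one arm only.

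Selection could add to it. The opening summary says that at this site a spinal may be offered "if the patient is not tolerating the procedure due to pain", and section 12 allows an attempt to be abandoned for discomfort. Rescued patients may therefore be those with the most first-attempt pain, and a last-attempt score would hide that pain. This is an inference: the protocol does not say that an attempt abandoned for pain counts as failed and leads to rescue.

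At stake is the reading of one secondary outcome. If the form takes no score after the first attempt, that score cannot be recovered later.

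**Working it through.** There is no planned figure to reproduce, because the documents give no effect size, SD or power for pain. The check has two parts.

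**1. The text side by side**

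- Section 19 ties the score to the procedure, in the singular.
- Section 9 uses the same word for everything that determines a 1-8 hour participation, which is the whole stay and not one maneuver.
- Section 14 has the form completed after the procedure ends. Section 12 has it completed at the time of the procedure. The two can be read together: one form, filled in at the bedside when the episode finishes, by an operator who belongs to the team.
- If the pain item is on that form (an inference), the likely result is one score per patient for the whole episode.
- Against this, the opening summary also uses the word for the first attempt alone. The reading is plausible but not conclusive.

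**2. How much the choice could matter (illustration)**

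From the documents: total N = 100 and alpha = 0.05. Assumed: 50 per arm, SD 2.5 for every summary, and second-attempt pain in Group 2 equal to Group 1 pain. Also assumed:

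- D, the first-attempt gap between arms: 1, 2 or 4 points.
- r, the share of Group 2 rescued: 0.2, 0.4 or 0.6.
- d, the extra first-attempt pain of rescued over non-rescued patients: 0 or 1 point.

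Arm difference by what is scored:

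- First attempt: D
- Average of both attempts: D - (r/2)(D + (1-r)d)
- Last attempt: (1-r)(D - r·d)

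Worked case, D = 2, r = 0.4, d = 0: average = 2 - 0.2 × 2 = 1.6; last = 0.6 × 2 = 1.2. With d = 1: average = 2 - 0.2 × 2.6 = 1.48; last = 0.6 × 1.6 = 0.96.

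Difference, with two-sided t-test power in brackets:

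| D | d | r | First | Average | Last |
|---|---|---|---|---|---|
| 1 | 0 | 0.2 | 1.0 (51%) | 0.90 (43%) | 0.80 (35%) |
| 1 | 0 | 0.6 | 1.0 (51%) | 0.70 (28%) | 0.40 (12%) |
| 2 | 0 | 0.2 | 2.0 (98%) | 1.80 (95%) | 1.60 (89%) |
| 2 | 0 | 0.4 | 2.0 (98%) | 1.60 (89%) | 1.20 (66%) |
| 2 | 0 | 0.6 | 2.0 (98%) | 1.40 (79%) | 0.80 (35%) |
| 2 | 1 | 0.4 | 2.0 (98%) | 1.48 (83%) | 0.96 (48%) |
| 2 | 1 | 0.6 | 2.0 (98%) | 1.28 (72%) | 0.56 (20%) |
| 4 | 0 | 0.4 | 4.0 (>99%) | 3.20 (>99%) | 2.40 (>99%) |
| 4 | 0 | 0.6 | 4.0 (>99%) | 2.80 (>99%) | 1.60 (89%) |

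The loss of power depends on the assumed gap. At 4 points it hardly matters which attempt is scored. At 1 point power is low whichever is scored. Only around 2 points does the choice decide whether a difference is likely to be detected. A smaller difference under another definition is also not bias: a patient spared pain by a rescue spinal did have a less painful last attempt.

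**Would a stricter rule be better?** One candidate is to score each attempt and analyze the worst. Only Group 2 can supply two scores, so its mean is pushed up by r × E[max(0, second - first)]. Take D = 2 and a correlation of 0.5 between attempts, so the SD of the difference is 2.5. For d = 0 the expectation is 2.5 × φ(0.8) - 2 × Φ(-0.8) = 0.724 - 0.424 = 0.30, which gives 0.06 at r = 0.2 and 0.18 at r = 0.6. With d = 1 the range is 0.03 to 0.14. This is small, but it favors Group 1. The rule would also mean 50 × r = 10 to 30 extra questions, asked between attempts by someone who would have to be named.

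**The case for a change.** The strongest case for acting is that the gap is plain on the text and one-sided. It touches a benefit the protocol itself names, and it would be cheap to close: a short paragraph and perhaps one extra field. A first-attempt score not taken at the time is lost. Even if the form scores each attempt, the analysis section does not say which value is compared.

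Much of this stands. No available section assigns the score to an attempt, and if pain is lower under spinal, a last-attempt score shrinks the difference whenever anyone is rescued. The discomfort criterion for abandoning an attempt makes that mechanism credible.

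What does not stand is the step from missing detail to a misleading result. That step needs a form that leaves the item open, and patients or staff choosing the reference attempt case by case. The documents show neither. A short application of this kind normally leaves item wording to the attached form, and that form's absence here is not a gap in the plan. If it does score each attempt, the authors can report both values and say which is which.

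**Conclusion.** No change to the plan is called for. The score's reference period is unstated in the available text, but the sensible reading, one rating of the whole episode, gives a valid comparison of immediate spinal with spinal only after failure. That is the comparison the trial was designed to make. Per-attempt scoring with a worst-score summary would answer a somewhat different question, bring a small asymmetry of its own and add a bedside task, so it is a preference and not a correction.

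The size is unknown. With an assumed 2-point gap and 20-60% rescued, the same patients could show a difference from 2.0 points (first attempt) down to 0.8 (last attempt, equal first-attempt pain) or 0.56 (last attempt, rescued patients 1 point worse). These figures rest on an assumed gap, SD, rescue share and equal allocation.

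The conclusion rests on two things that the documents do not settle: that the score is taken once for the whole episode, or per attempt on the form, and that it is taken the same way for every patient. If the form proved to score only the last attempt, the discomfort result should be read as pain at the final attempt and not as the pain of the strategy. Only a secondary outcome is involved.

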The primary outcome will be the success rate of external cephalic version to cephalic presentation. Secondary outcomes will include: time from procedure to delivery, mode of delivery, patient discomfort, adverse events during procedure (ie.fetal bradycardia, emergent cesarean section, abruption), neonatal outcomes (ie. birthweight, Apgars, cord pH, NICU admission). The external cephalic version procedure may be terminated in any patient at any time regardless of this study in the event of persistent fetal heart rate abnormalities, maternal request, or any other adverse findings that the physician believes is an indication that the procedure must be terminated.

Protocol Was Already Approved by the Icahn School of Medicine at Mount Sinai (ISMMS) Institutional Review Board (IRB) Under a Different Principal Investigator No

Protocol Was Previously Submitted to an External(non-ISMMS) IRB No

4. Research Personnel

Name/Department	Role/Status	Contact	Access	Signature Authority	Phone	Email
[name] / Obstetrics/ Gynecology	PI /	Yes	SIGNAUTH			
[name] / Obstetrics/ Gynecology	Co-Investigator /		EDIT			
[name] / Obstetrics/ Gynecology	Co-Investigator /		EDIT			
[name] / Obstetrics/ Gynecology	Co-Investigator /		EDIT			
[name] / Obstetrics/ Gynecology	Co-Investigator /		EDIT			
[name] / Anesthesiology	Co-Investigator /		EDIT			
[name] / Anesthesiology	Co-Investigator /		EDIT			
[name] / Anesthesiology	Co-Investigator /		EDIT			

5. Sites

Site Name Mount Sinai West

Other External Site Name

Contact Details

Approved 0

Approval Document

Funded By Mount Sinai 1

Reviewed By Mount Sinai IRB

Other IRB

6. Subjects - Enrollment

Site Name	Mount Sinai Roosevelt
Subjects To Be Enrolled	
100	
Total	100

7. Subjects - Setting and Resources

Setting of Human Research Other

Specify Other Setting of Human Research

Labor and Delivery unit at Mount Sinai West hospital.

Total Number of Subjects Needed 100
To Complete Study

Feasibility of Meeting Recruitment Goals

From 2012-present we have attempted approximately 89-115 external cephalic versions a year. Each year we have been increasing in numbers, with 115 patients in 2015. These numbers only include patients who had an attempted ECV and does not include patients that were scheduled for ECV but the procedure was not performed for various circumstances. Given this information we believe that it will take approximately 1-2 years to recruit 100 patients.

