Accessing Data Yes

Receipt or Transmission of Data Yes

Holding Code That Can Be Linked to Identity of Participants No

Research Personnel Responsible for: [name]

Accessing Data Yes

Receipt or Transmission of Data Yes

Holding Code That Can Be Linked to Identity of Participants No

Research Personnel Responsible for: [name]

Accessing Data Yes

Receipt or Transmission of Data Yes

Holding Code That Can Be Linked to Identity of Participants No

Research Personnel Responsible for: [name]

Accessing Data Yes

Receipt or Transmission of Data Yes

Holding Code That Can Be Linked to Identity of Participants No

Research Personnel Responsible for: [name]

Accessing Data Yes

Receipt or Transmission of Data Yes

Holding Code That Can Be Linked to Identity of Participants No

Research Personnel Responsible for: [name]

Accessing Data Yes

Receipt or Transmission of Data Yes

Holding Code That Can Be Linked to Identity of Participants No

Research Personnel Responsible for: [name]

Accessing Data	Yes
Receipt or Transmission of Data	Yes
Holding Code That Can Be Linked to Identity of Participants	No

Duration Data Will Be Stored

Data will be stored until the data is analyzed, within 1 year from study completion.

Steps That Will Be Taken to Secure the Data During Storage, Use, and Transmission

The study investigators will collect medical information about the subject over the course of the study. Study data will be entered into a de-identified research database, using a unique code numbering system. A code number linked to subject identity will be used instead of names. The code number will not be derived from any patient identifiers, such as patient name or medical record number. The record linking the subjects' name with their assigned codes will be kept on the computer in a separate secure folder. All files are password protected on a secure server.

Data Analysis Plan Including Any Statistical Procedures

Continuous variables will be analyzed using two tailed T-test and categorical variables will be analyzed using Pearson Chi Square test. Logistic regression will be used to adjust for confounders. A p-value <0.05 will be considered significant.

22. Data - Safety Monitoring

More Than the Minimum Data Safety Monitoring Will Be Done No

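### Do the below-threshold entries for Apgar and cord pH, and the missing birthweight entry, in the data list mean that the neonatal outcomes will be recorded too coarsely?

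*Combined protocol and SAP*

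**What the plan says.** Section 3 (Primary and Secondary Study Endpoints) makes the success of the version the primary outcome. Among the secondary outcomes it lists "neonatal outcomes (ie. birthweight, Apgars, cord pH, NICU admission", with no cut-point and no Apgar time point.

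Section 19 (Data - Collection) describes the health information to be handled. Its non-primary items open with "Other information that will be recorded includes", and the delivery and neonatal part reads "delivery mode, 5 minute, Apgar score <7, arterial cord pH <7.2, NICU admission". The comma after the word minute appears to be a slip for the 5-minute Apgar. Birthweight is not in that run, nor in the sentence on baseline items: "Demographic data will also be collected such as age, race, BMI, parity, and medical disease".

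Section 12 (Description of the Source Records) says where the rest comes from: "All other data about delivery and demographics will be collected after the procedure using labor and deliveries' electronic medical record system (Peribirth".

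Section 21 (Data Analysis Plan) assigns tests by type of variable: "Continuous variables will be analyzed using two tailed T-test", with Pearson chi-square for categorical variables. It does not say which type Apgar or cord pH is.

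**The concern.** Of the four neonatal outcomes in section 3, only NICU admission appears in the same form in section 19. Apgar and cord pH appear there with a threshold attached, and birthweight does not appear. Read literally, section 19 could mean that the database holds two yes/no flags and no birthweight.

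That would matter for two reasons. A flag can be derived from a number, but a number cannot be recovered from a flag. And in a trial of 100 patients, dichotomising a continuous measurement such as pH makes an already imprecise comparison less precise. Sections 12 and 20 add some urgency, because the linked code and data are to be deleted once analysis is finished.

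**Working it through.** **The plan's own figure.** There is none to reproduce. The documents give no event rate, standard deviation, effect size or power for any neonatal outcome.

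**Setting the sections side by side.**

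| Outcome in section 3 | In the section 19 list | Source under section 12 | Test under section 21 |
|---|---|---|---|
| NICU admission | Listed | Electronic record | Chi-square |
| Apgars | 5-minute, below 7 | Electronic record | Chi-square if a flag; t-test if treated as continuous |
| Cord pH | Arterial, below 7.2 | Electronic record | Chi-square if a flag; t-test if numeric |
| Birthweight | Not itemised | Electronic record | t-test |

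Time from procedure to delivery, another secondary outcome in section 3, is not itemised in section 19 either, although sections 12 and 15's counterpart on data protection (section 20) keep dates of service. The list is therefore not a complete inventory of the outcomes, and absence from it does not show that an item will go uncollected.

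**What would be lost if pH were stored only as a flag.** The inputs are the total of 100 patients (section 7); 50 per arm (assumed, as no allocation ratio is stated); complete pH data and a normal distribution (assumed); and a proportion q below 7.2 (assumed, 5% to 50%).

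The information kept by a flag about a mean shift, relative to the numeric value, is φ(z_q)² / [q(1 − q)], where φ is the standard normal density and z_q its q-quantile. The half-width with numeric pH is 1.96 × √(2/50) = 0.392 SD. With the flag it is 0.392 divided by the square root of the information kept.

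| q | Information kept | Half-width with flag (SD) |
|---|---|---|
| 5% | 0.224 | 0.392/√0.224 = 0.828 |
| 10% | 0.342 | 0.392/√0.342 = 0.670 |
| 20% | 0.490 | 0.392/√0.490 = 0.560 |
| 50% | 0.637 (maximum) | 0.392/√0.637 = 0.491 |

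The information kept falls below one half when q is under about 21%.

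A separate two-proportion calculation points the same way. It uses 50 per arm, two-sided 5%, and a 0.56 SD shift that moves the other arm towards lower values. Power on the numeric value is about 80%. On the flag it is about 21%, 33%, 44% or 55% if 2%, 5%, 10% or 20% of the better arm lies below the cut.

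**Limits of these figures.** At 5% and 10% the expected counts are only 50 × 0.05 = 2.5 and 50 × 0.10 = 5 per arm, where a large-sample efficiency is a rough guide. The figures concern pH only. They do not carry over to Apgar, which is ordinal, or to birthweight, which nobody proposes to dichotomise. They measure precision for a mean shift. If the intended outcome is the proportion below 7.2, that is a different quantity, and lower precision for a mean is not a fault in it.

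**Whether the condition is met.** The loss arises only if the number is not stored, and no section says so. Section 19 introduces its items with an inclusive verb, and whoever abstracts the record must see the pH and the Apgar score to apply either cut.

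**The case for a change.** The best case for a change is that no section settles the matter. Section 12 names no neonatal field, and section 21 does not assign Apgar or pH to a test, so the same outcome could be analysed as a mean or as a proportion, with the choice made after seeing the data. The questionnaire is not reproduced, but sections 12 and 14 describe it as a record of the procedure completed by the operator afterwards, so it is unlikely to hold neonatal values. Naming three numeric fields would cost little, since the delivery record is being opened anyway, and the thresholds could still be reported.

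Some of this stands. The two sections do not match item for item, the storage format is unstated, and storing the number is better practice because it leaves both analyses open.

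The step from there to a needed change does not stand. Section 3 already names birthweight, Apgars and cord pH as outcomes, and section 12 already provides the route to them. The thresholds in section 19 can reasonably be taken as completing section 3. The latitude between a mean and a proportion touches two secondary outcomes and leaves the trial's main conclusion alone. The planned deletion comes only after collection and analysis are complete, so a value missed at first abstraction can be looked up while the link still exists.

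**Conclusion.** No change is called for. The mismatch between sections 3 and 19 is real but is missing detail in an institutional form, and no stated rule or figure is wrong. Followed as written, with outcomes from section 3, data from the electronic record under section 12 and the test matched to the type of variable under section 21, the plan still gives sound neonatal comparisons. A team preparing its extraction sheet would ordinarily enter birthweight and the numeric pH and Apgar values and derive the two thresholds from them.

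The possible loss is confined to cord pH stored only as a flag and analysed for a mean shift. It would keep between 22% and 64% of the information, assuming normality, complete data and 5% to 50% of babies below the cut; the half-widths also assume 50 per arm. The documents do not establish that this would happen. The primary outcome, NICU admission and procedure complications are unaffected in any case.
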